Negative Urgency will be assessed using the Urgency, Premeditation, Perseverance, Sensation Seeking, Positive Urgency, Impulsive Behavior Scale.⁷⁶ Participants will complete visual analog scale (VAS) questions related to spontaneous pain and pain with movement, with each line being anchored with 'none' on the left and 'worst imaginable' on the right.⁷⁷ Additionally, participants will complete several pain experience visual analog scales (PEVAS); the PEVAS includes seven 10-cm lines that measure a different component of the pain experience (i.e. depression, anxiety,

frustration, fear, anger, pain intensity, pain unpleasantness) with a written description of 'none' on the left and 'worst imaginable' on the right. The PEVAS will measure pain-related negative affect, and participants will provide their rating by placing a mark along each line. Expectancies of muscle soreness from the exercises involved in this study will be assessed with a VAS-style question anchored by 'no muscle soreness' and 'most intense muscle soreness imaginable.' In addition, expectancies of analgesia from alcohol and marijuana, as well as urge to consume alcohol and marijuana, will also be measured using VAS-style questions, with lines being anchored by 'no pain relief at all' and 'complete pain relief' for expectancies of analgesia and lines being anchored by 'no urge' and 'very strong urge' for urge-related questions. History of self-medication behaviors will be assessed using separate VAS-style questions measuring likelihood of using alcohol or marijuana when experiencing pain in the past. Each line will be anchored by 'none of the time' and 'all of the time'. Other measures will assess alcohol use patterns (Alcohol Use Disorders Identification Test,⁷⁸ Alcohol Use Questionnaire⁷⁹), marijuana use patterns (Cannabis Use Disorder Identification Test, Revised,⁸⁰ Daily Sessions, Frequency, Age of Onset, and Quantity of Cannabis Use Inventory⁸¹), and use of other substances (NIDA Modified Alcohol, Smoking and Substance Involvement Screening Test,⁸² Fagerstrom Test for Nicotine Dependence⁸³). Finally, a single-item question will measure frequency of simultaneous alcohol and marijuana use behaviors over the past 12 months.⁸⁴

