Participants who continue to qualify following completion of screening procedures and agree to proceed will be assigned to either the *DOMS* or *Sham DOMS* group. Assignments will be made according to a participant's unique subject identifier using a spreadsheet listing group assignment in pseudo-random order using the Excel random number function.

Participants will then complete the Alcohol Purchase Task (APT), Marijuana Purchase Tasks, (MPT), and DOMS or sham DOMS induction procedures. They will also be will be scheduled for a second lab session 48 hours later so that potential changes in DOMS-associated alcohol and marijuana demand can be investigated. Participants who complete the screening but either do not qualify or decide not to proceed will be paid \$15 via gift card. Those who do qualify and proceed with the study will be paid \$50 at the end of the first lab visit and \$15 at the end of the second lab visit. For the daily surveys, compensation was provided as a function of the number of surveys completed, with a maximum of \$30 for participants who completed 5/7 or more of their assessments (see "Daily Measures" section for additional information). We will also ask whether their DOMS (if any) has resolved with the daily measures. Additionally, participants who refer an individual to the study that attends the screening session will also receive \$20 per person referred. The referee(s) will be responsible for contacting the study team via phone or email in order to schedule the session. The referrer will receive the \$20 bonus once the person they refer attends their screening session, whether or not they eventually decide to participate. All participants who provide informed consent will be eligible to refer participants to the study regardless of whether they qualify to proceed after screening procedures.

Alcohol Purchase Task (APT) and Marijuana Purchase Tasks (MPT)

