Both the APT and MPT will be administered on REDCap during the first lab session prior to DOMS induction and during the second lab session (48 hours post DOMS induction). In the APT, participants are provided with a set of instructions, including a definition of a standard drink, and asked how many standard drinks they would consume at 21 prices, ranging from free to \$30/drink (e.g. "How many drinks would you consume if they were \$1.00 each?"). Procedures for the MPT are virtually identical, except a standard definition of the number of hits of marijuana in one joint is provided, and participants are asked how many hits of marijuana they would take at a series of escalating price points ranging from free to \$10/hit. Participants will also complete an adapted form of the MPT that allows for differences in preference for various marijuana-based products and modes of administration. From these data, the following indices of alcohol and marijuana demand will be generated: intensity (consumption of hits/drinks when free); breakpoint (the first price at which consumption was zero); O_{max} (maximum expenditure on alcohol and marijuana hits); P_{max} (price where demand becomes elastic); elasticity (rate of change in consumption with changes in price). Studies have demonstrated that these indices can be reduced to two latent factors: persistence (maintaining consumption despite increasing price) and amplitude (maximum consumption and price levels). Persistence is composed of elasticity, P_{max} , breakpoint, and O_{max} , while amplitude is composed of intensity and O_{max} .⁸⁵⁻⁸⁶

Isometric Strength Testing and DOMS Induction

Maximum voluntary contraction (MVC) of elbow flexion strength will be tested using a BiodeX System Isokinetic Dynamometer (BiodeX Medical Systems, Shirley, NY), and torque values obtained from this testing will be used to inform exercise protocols. The participant will first be seated within the testing apparatus with a stabilizing strap attached proximal to the elbow joint. The participant will then move through their available range of motion in the elbow flexion and extension. The device will be locked at 90 degrees of elbow flexion, and the participant will be instructed to build maximal flexion force while holding onto the grip handle of the machine. Once peak effort is achieved, the participant will be instructed to relax, the device will be released, and the subject will be returned to a neutral position.

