Figure 1. BiodeX setup for isometric strength and DOMS.

DOMS-inducing exercise protocol. To perform the dynamic fatiguing exercise bout, the participant will be seated in the BiodeX machine in order to isolate elbow flexion. The participant will perform the isometric strength test (described above). Following 60 seconds of rest after the isometric test, participants will complete an exercise protocol consisting of eccentric (elbow straightening/biceps lengthening) exercises designed to induce DOMS at the biceps. **Participants in the DOMS group will perform 3 sets of 15 repetitions at a speed of 60°/s. Participants in the Sham DOMS group will complete one set of 15 concentric (elbow flexion/biceps shortening) repetitions at**

a resistance set to 30% of their maximum voluntary contraction, which is unlikely to induce significant DOMS.

DOMS-related Pain Measures

Upon arriving in the laboratory for their second study session, participants will complete several measures regarding pain associated with the exercise protocol.

1. Pain Experience: Pain experience visual analog scales (PEVAS) include seven 10-cm lines that measure a different component of the pain experience (i.e. depression, anxiety, frustration, fear, anger, pain intensity, pain unpleasantness) with a written description of 'none' on the left and 'worst imaginable' on the right. The PEVAS will measure pain-related negative affect, and participants will provide their rating by placing a mark along each line.

2. Pain with Movement: Participants will also rate pain during elbow extension and elbow flexion using the same scale. This will give ratings of both spontaneous pain and pain with movement.

Daily Measures

Participants will receive instructions related to the daily electronic diary following DOMS induction. These measures will primarily be used evaluate the pain associated with DOMS and assess alcohol and marijuana use following the exercise protocol.

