Hypotheses for DOMS-related changes in alcohol and marijuana demand indices (persistence and amplitude) will be assessed using separate 2 (group: DOMS vs. sham DOMS) x 2 (sex: men vs. women) x 2 (race: White vs. Black) x 2 (time: visit 1 vs. visit 2) repeated measures analysis of variance (ANOVA). Identical ANOVAs will examine changes in marijuana demand indices.

Aim 2: Identify psychosocial factors associated with change in demand for alcohol and marijuana after DOMS induction.

To test the hypothesis that negative affect mediates the relationship between DOMS pain and increased alcohol and marijuana demand, Pearson correlations will be conducted to examine continuous relationships between measures of pain, pain-related negative affect (e.g. pain experience VASs), and change in alcohol and marijuana demand. A series of linear regressions will then be conducted to examine 1) the effect of group (DOMS vs. sham DOMS) on change in alcohol and marijuana demand, and 2) the effect of group and pain-related negative affect on change in alcohol and marijuana demand. We will test the significance of indirect effects of pain-related negative affect using PROCESS, a custom macro in SPSS.

To examine the hypothesis that greater expectancy of analgesia from marijuana or alcohol use, higher negative urgency, and history of self-medication behaviors will predict greater change in demand, a simultaneous multiple linear regression analysis will be conducted with these variables as predictors in the model.

Power Analysis

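### Cheap improvement: draw and reveal a concealed assignment only after the baseline purchase tasks, which the protocol now places after assignment

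*Combined protocol and SAP*

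**What the plan says.** The order is set in section 6, at the end of Screening Measures. Assignment comes first: "Participants who continue to qualify following completion of screening procedures and agree to proceed will be assigned to either the" DOMS or sham DOMS group. The next paragraph continues: "Participants will then complete the Alcohol Purchase Task (APT), Marijuana Purchase Tasks, (MPT), and DOMS or sham DOMS induction procedures".

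The allocation is looked up by "unique subject identifier using a spreadsheet listing group assignment in pseudo-random order using the Excel random number function". The text mentions no concealment, masking, allocation ratio, blocks or strata, and no list holder.

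The section on the purchase tasks fixes their timing only relative to the exercise: "Both the APT and MPT will be administered on REDCap during the first lab session prior to DOMS induction". Under Isometric Strength Testing and DOMS Induction, both arms do the same strength test. "Following 60 seconds of rest after the isometric test, participants will complete an exercise protocol", and the arms differ only in the repetitions of that exercise.

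The other self-reported baselines are screening measures and so precede assignment. They include pain experience, expected soreness, expected analgesia, "as well as urge to consume alcohol and marijuana, will also be measured using VAS-style questions".

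In the Data Analysis Strategy, Aim 1 crosses group with "2 (sex: men vs. women) x 2 (race: White vs. Black) x 2 (time: visit 1 vs. visit 2) repeated measures analysis of variance". Aim 2 regresses change in demand on group, and then on group and negative affect together. The first of these estimates "the effect of group (DOMS vs. sham DOMS) on change in alcohol and marijuana demand".

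**The concern.** Visit 1 demand is half of every change score. The purchase tasks are hypothetical self-reports, and a participant who knows that a hard or an easy exercise is minutes away might answer them differently. Such a shift would look like a DOMS effect of opposite sign, and the planned analysis could not separate the two.

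The stated order opens this possibility without any visible gain. No step between assignment and the exercise repetitions depends on the arm, and the remaining self-reported baselines are already collected before assignment. Only the baseline of the main outcome is left after it.

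**Working it through.** **Inputs.** From Power Analysis: N = 56, alpha .05, power .80, correlation between visits r = 0.5, pilot partial eta squared .08 for amplitude. From Data Analysis Strategy: 2 x 2 x 2 between-subject cells and 2 visits. Assumed: 28 per arm (no ratio is stated), a two-sided test, and the size b of any baseline shift, for which the documents give no value.

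**The plan's own figure.** For a within-between interaction, lambda = f² x N x m / (1 − r), with df1 = (k − 1)(m − 1) and df2 = (N − k)(m − 1). With f = √(.08/.92) = 0.295, k = 8 and m = 2:
- N = 48: lambda = 16.70, power .791
- N = 49: lambda = 17.04, power .803
- rounded up to a multiple of 8, N = 56: lambda = 19.48, power .871

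So 56 is reproduced. The choice of f and of 8 groups is inferred, because the protocol does not state them.

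**Where a shift goes.** Change = visit 2 − visit 1. If everyone in the DOMS arm shifts by b at visit 1, each of the four DOMS cells has its mean change moved by −b, and the sham cells do not move.
- Group x time: the contrast moves by −b.
- Group x sex x time: (−b) − (−b) = 0. The same subtraction gives 0 for group x race x time and for the four-way contrast.
- Aim 2 regressions: the coefficient of group moves by −b, both alone and with negative affect in the model. The coefficient of negative affect given group does not move.
- The simultaneous regression on expectancy, negative urgency and self-medication history uses predictors measured before assignment, so a uniform shift is unrelated to them.

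A simulation with 7 per cell and b = 0.3 SD agrees: group x time rejects about 20% of the time with no true effect, and the three interactions about 5%.

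**Sensitivity of group x time.** In units of the SD at one visit, SD(change) = √(2(1 − 0.5)) = 1.00. The standard error is 1.00 x √(2/28) = 0.267. With df = 56 − 8 = 48, the difference detectable with 80% power is 0.764 SD. The noncentrality is b / 0.267.

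| Assumed shift b (SD) | Noncentrality | Share of 0.764 SD | Type I error | Power for a true 0.764 SD effect if b opposes it |
|---|---|---|---|---|
| 0 | 0 | 0% | 5.0% | 80% |
| 0.05 | 0.19 | 7% | 5.4% | 74% |
| 0.1 | 0.37 | 13% | 6.6% | 68% |
| 0.2 | 0.75 | 26% | 11.4% | 54% |
| 0.3 | 1.12 | 39% | 19.6% | 40% |

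**Optional stratification.** The table gives the variance of the four-way contrast relative to exactly 7 per cell, simulated at N = 56. The recruitment mixes are assumptions.

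| Recruitment mix | Independent draws | Shuffled 28:28 list | Sex-race strata, blocks of 4 and 6 |
|---|---|---|---|
| Even | 1.180 | 1.150 | 1.070 |
| 30% Black | 1.482 | 1.454 | 1.331 |
| 14 per stratum | 1.095 | 1.067 | 1.005 |

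The cut in standard error is 1 − √(ratio). The smallest is 1 − √(1.005/1.067) = 2.9% and the largest is 1 − √(1.331/1.482) = 5.2%. At 30% Black, some cell still has 3 or fewer participants in 70% of trials with stratified blocks (89% with independent draws). Someone tracking each stratum could guess the next arm about 68% of the time, against about 58% with a shuffled list and 50% with independent draws.

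**The case against.** The strongest reply is that the harm needs a fact the documents do not supply. Being assigned is not the same as being told, and a list entry that nobody reveals cannot change an answer. Calling the control a sham is at least compatible with participants not being told. The study flowchart (Figure 2) is not shown and the consent pages were removed, and either might settle the timing. This stands: a reader might infer that the baseline is biased, and the documents do not support that.

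A reader might also infer that every analysis is exposed, because visit 1 demand enters them all. That does not hold either. A uniform shift cancels from the terms that carry the race and sex predictions of Aim 1. They are affected only if the shift itself differs by sex or race.

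Third, the assumed shifts have no source in the documents, and at 0.05 SD almost nothing happens. This also stands, so the table is a sensitivity range and not a forecast.

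Fourth, reordering alone may protect nothing. With a list keyed to the subject identifier, the arm is fixed once the identifier is issued, and session staff who can read the list know it. This is right, and it makes concealment the effective part of the fix.

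What remains is that the protocol states an order that exposes the baseline of its main outcome to no visible purpose and describes no concealment.

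**Conclusion.** The point holds as a cheap improvement. The stated order puts the baseline purchase tasks after assignment, and no earlier step needs the arm. It is an avoidable risk to the overall group x time contrast and to the group coefficients in the Aim 2 regressions. The interactions with sex and race are not at risk from a uniform shift.

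The size is unknown. Between 0.05 and 0.3 SD, the group x time type I error would run from 5.4% to 19.6%, assuming 28 per arm, r = 0.5, df = 48 and a shift confined to one arm.

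The lack of stratification is a smaller matter. A reader might infer that uneven cells bias the interactions, but sex and race are already in the model. Chance imbalance therefore costs precision and does not by itself bias them.

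**What to change.** Rewrite the assignment step in section 6 in this order:
1. Confirm eligibility and agreement to proceed, as already planned.
2. Complete the baseline APT and MPT.
3. Only then draw and reveal the next concealed assignment, for example in REDCap, which the study already uses.

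State that the list is held by someone who does not run the session and that the arm cannot be read from the subject identifier. Reordering without this concealment is not enough. If staff already withhold the arm until the exercise, say so in the protocol and name the role that holds the list.

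The cost is a small change to how the list is held and released, within the same visit. It does not mask visit 2, where soreness may reveal the arm.

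Optional, and not part of the main fix: stratify the list by sex and race in randomly varied blocks of 4 and 6, with block sizes withheld from enrolling staff. Demographics, including racial identity, are collected before assignment, so the cost is one-time list preparation. The gain is about 3-5% in the standard error of the four-way contrast. It does not cure a skewed recruitment mix, and it makes the next arm easier to guess. The main fix should be kept even if this step is declined.

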Aim 1. Determine impact of DOMS pain on demand for alcohol and marijuana and examine race and sex as moderators of this relationship.

We predict that those who undergo the DOMS induction paradigm will show greater increases in alcohol and marijuana demand than participants in the sham DOMS control group. We also predict an interactive effect of race and sex on DOMS-related changes in alcohol and marijuana demand, such that increases may be greater in White men than Black women and men, as well as White women.

Aim 2. Identify psychosocial factors associated with change in demand for alcohol and marijuana after DOMS induction.

Consistent with current evidence,^{42, 67} we predict that pain-related negative affect will mediate the association between DOMS-related pain and increased demand for alcohol and marijuana. We also predict that greater expectancy of analgesia from marijuana or alcohol use, higher negative urgency, and history of self-medication behaviors will predict greater change in alcohol and marijuana demand.

6. Research Plan:

Participants

We will recruit participants aged 21 years and older who are regular co-users of alcohol and marijuana (i.e., concurrent or simultaneous use at least 2-3 times per week over the past 6 months). Extent of co-use will be determined using the Alcohol Use Disorders Identification Test (AUDIT) and Cannabis Use Disorder Identification Test, Revised (CUDIT-R). A research team member will inform participants of inclusion and exclusion criteria via email or the phone. If an individual believes they meet all study criteria, they will be scheduled for the first study session (see Phone and Email Scripts for details). We will review all inclusion and exclusion criteria one additional time with participants before initiating the Informed Consent process.

Inclusion/Exclusion Criteria

Detailed inclusion/exclusion criteria are provided in Table 1.

Table 1. Inclusion and exclusion criteria
Inclusion Criteria 
• Aged 21-65 years;• English-speaking• Self-identify as White/Caucasian or Black/African American• Own a smartphone with cellular/data plan• Regularly co-use alcohol and smoked marijuana as indicated by scores of ≥ 3 on item 1 of the CUDIT-R and AUDIT.• Willing and able to give informed consent

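### The Aim 2 mediator is not scored, its listed lines include pain itself, and the mediation model has no pain term, so an effect of pain on demand can be reported as mediation by negative affect

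*Combined protocol and SAP*

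**What the plan says.** Section 5 (Aim 2) predicts that "pain-related negative affect will mediate the association between DOMS-related pain and increased demand for alcohol and marijuana". Pain is therefore the upstream variable and affect the proposed carrier.

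Section 6 describes the PEVAS twice, under Screening Measures and under DOMS-related Pain Measures. Both places list the same seven lines: "depression, anxiety, frustration, fear, anger, pain intensity, pain unpleasantness". Both then assign the instrument, with no line set aside, to negative affect: "The PEVAS will measure pain-related negative affect".

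Data Analysis Strategy (Aim 2) begins with Pearson correlations between measures of pain, "pain-related negative affect (e.g. pain experience VASs), and change in alcohol and marijuana demand". Two regressions follow. The second, which carries the mediation test, estimates "the effect of group and pain-related negative affect on change in alcohol and marijuana demand". The indirect effect is tested with PROCESS. No section defines a PEVAS total, an emotion subscale or a pain term for these regressions.

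**The concern.** Aim 2 asks whether emotion carries the effect of DOMS pain on demand. The induction exists to raise pain. If pain intensity and unpleasantness are part of the mediator score, the group-to-mediator path is partly a manipulation check. The mediator-to-demand path also absorbs any direct effect of pain. A significant indirect effect could then mean that affect matters, or only that pain matters, and the planned model could not tell which.

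The missing pain term is a second and separate route to the same error. Even a pure emotion score can stand in for pain if it rises with pain and pain is not in the regression. The conclusion at risk is the Aim 2 mediation claim. The Aim 1 ANOVAs are unaffected.

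**Working it through.** **Plan's own figures.** The plan gives no figure for the mediation analysis. The only input taken from it is N=56 (Power Analysis). That number can be reached from the pilot partial eta squared of .08: f = sqrt(.08/.92) = .295, 8 between-subject cells, 2 times, correlation .5, alpha .05, power .80 give N=49, rounded up to 56 for equal cells. The effect size and cell count are inferred, and nothing below depends on them.

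**What the model estimates.** Let a be the effect of group on the mediator M, and b the effect of M on demand change given group. The indirect effect is a × b. If M is the mean of all seven lines, then a = (5·a_emotion + a_intensity + a_unpleasantness)/7. Suppose DOMS shifts only the two pain lines, each by d SD. Then a = 2d/7, although no emotion has moved. Assume correlations of .5 among emotion lines, .7 between the pain lines and 0 across. The variance of the seven-line sum is 5 + 20(.5) + 2 + 2(.7) = 18.4, so M shifts by 2d/sqrt(18.4) of its own SD: 0.47 for d=1 and 0.93 for d=2.

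**Simulation 1: emotions do not shift with DOMS.** 28 per arm, 4,000 trials per scenario, d from 1 to 2, pain correlated .3 to .5 with demand change, emotion without effect on demand, joint significance of a and b as a stand-in for the PROCESS bootstrap.
- Seven-line mean: false indirect effect in 6% to 33% of trials when pain and emotion lines are uncorrelated, and in 12% to 63% when they correlate .3.
- Five emotion lines: 0.2% to 1.7%. This low rate is largely built in, because a is zero by assumption.

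**Simulation 2: emotions track pain.** N=56, 1,500 trials per scenario, d=1.5, affect correlated r with pain within group and shifting with it, affect still without effect on demand, Monte Carlo interval for a × b. The pain term is the mean of intensity and unpleasantness.

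| r (pain, affect) | Pain-demand slope | Seven lines | Five emotion lines | Five lines + pain in model |
|---|---|---|---|---|
| 0 | .3 | 5.2% | 0.2% | 0.2% |
| 0 | .5 | 9.4% | 0.3% | 0.3% |
| .3 | .3 | 19.9% | 2.9% | 1.7% |
| .3 | .5 | 41.6% | 6.3% | 1.5% |
| .5 | .3 | 32.7% | 13.8% | 3.8% |
| .5 | .5 | 65.7% | 26.1% | 3.7% |
| .7 | .3 | 45.3% | 31.2% | 5.7% |
| .7 | .5 | 80.9% | 60.9% | 5.7% |

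With a slope of zero the seven-line rate is 2.3% to 6.5%, so the excess comes from the effect of pain. The simulation standard error at 5% is sqrt(.05 × .95/1500) = 0.6 percentage points, so 5.7% is not distinguishable from the nominal level.

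**Simulation 3: the line structure of simulation 1, with the pain shift carried to the emotion lines in proportion to r = .3 to .5.** The five-line mean alone gives about 4% to 76%; with pain in the model, about 1% to 5%.

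Dropping the two pain lines therefore removes the overlap but not the confounding by pain. The pain term does most of the remaining work.

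**The case against.** The strongest reply is that the plan never says the mediator is a seven-line score. The analysis section gives the scales only as an example ("pain-related negative affect (e.g. pain experience VASs"), in the plural, within the correlation sentence. It names measures of pain separately, and each line is described as measuring a different component. A reader might infer from the PEVAS sentence that a seven-line composite is planned. The documents do not support that: it is the literal reading of the construct statement, not a scoring rule. What remains is that the text assigns the whole instrument to negative affect twice, excludes nothing, and leaves the choice of lines open until data are in hand.

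A reader might also say that the mediator contains the exposure. In the regressions the exposure is assigned group. The overlap is with pain as the hypothesis's upstream variable.

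Pain unpleasantness can be argued to be affective. Pain intensity cannot, and it alone creates the overlap.

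Nor is the bias certain to favour the hypothesis. The high rates need a uniformly positive pain-demand slope. The pilot (Power Analysis) found DOMS effects on alcohol demand in opposite directions in men and women. With equal and opposite slopes by sex, an extreme assumption, the seven-line rate was 1% to 6%.

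Finally, part-whole inflation of the planned pain-affect correlation (1.7/sqrt(18.4) = .40 even if pain and emotion are independent) arises only if a PEVAS pain line is also the pain measure. Separate pain ratings are collected, and the plan does not say which will be used.

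**Conclusion.** The concern holds in this form: the mediator score is undefined, the text does not exclude the two pain lines, and the mediation regression has no pain term. As written, an effect of pain on demand can be reported as mediation by negative affect.

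The false-positive rates show direction and range and are not a forecast. They rest on assumed inter-line correlations, an assumed DOMS shift and an assumed positive pain-demand association. Under those assumptions the seven-line score is wrong in about 6% to 63% of trials when emotions stay put, and in up to 81% when they follow pain closely. A reader might conclude that scoring only the emotion lines solves the problem. It does so only if emotions do not follow pain; otherwise false mediation reached 61% and 76% in the two sets of runs. With pain modelled alongside, the rate stayed at about 6% or less.

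**What to change.** Under Screening Measures, DOMS-related Pain Measures and Data Analysis Strategy (Aim 2):
1. Define the mediator as the mean of the five emotion lines (depression, anxiety, frustration, fear, anger) at visit 2.
2. Reserve pain intensity, pain unpleasantness and pain with movement as pain measures, and name the one used in the correlations.
3. Require pain intensity (or the mean of intensity and unpleasantness, as simulated) as a parallel or preceding mediator in PROCESS, so that the pain and emotion paths are estimated separately. Choose the arrangement before the data are examined.

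The cost is a few sentences and one model term; all the measures are already collected. The emotion indirect effect will probably be smaller and less precise. Other things equal, the standard error of its demand path grows by 1/sqrt(1 − r²), where r is the within-group pain-emotion correlation: about 1.15 times at r=.5 and 1.40 times at r=.7. That is the price of separating the two paths.

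Adjusting for screening affect and visit 1 demand may be worthwhile, but it is a separate suggestion and does not address this overlap.
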